- Food amount booklet and two food record forms (stamped returned envelope provided as needed)
- Health assessment form for Chinese participants (Appendix F)
- Health questionnaire for Chinese participants and Chinese version attached (Appendix G)

Procedures:

1. An email (Appendix F) will be sent out to invite potential Chinese participants to participate in the Chinese Traditional Medicine assessment and Health Questionnaire survey.
2. The PPCCT research staff will meet the participant at the Vanderbilt Epidemiology Center or at the Nashville Chinese Baptist Church on the day scheduled for the health survey.
3. The PPCCT research staff member will describe the study protocol in lay terminology, including the purpose of the study and the study design.
4. The risks and benefits of the study are discussed prior to obtaining signatures on the consent form. The participant will be told that participation is voluntary.
5. The research staff will provide ample time for the participant to have questions answered prior to enrollment.
6. Obtain written informed consent.
7. The research staff will also provide the study participant with a copy of the consent form.
8. Health assessment will be performed and the collected information will be recorded on a Health Assessment Form for Chinese participants (Appendix F) by a PPCCT research staff.
9. Health questionnaire for Chinese Participants both in Chinese version and English version (Appendix G), two food record forms and a food amount booklet (Appendix F) will be administrated in person. A stamped return envelope will be provided if required.
10. A Thank you letter will be mailed to the participant after completion of the health survey.

4. Biological Specimen Collection Protocol

-- Rectal Biopsy

Rectal Biopsy Procedures and Initial Handling Protocol

Biomarkers measured from rectal biopsies will include Ki-67 (cellular proliferation), Bax (pro-apoptosis), COX2 (inflammation), and TRPM7 (Calcium/Magnesium absorption), pMLKL (necessary for the execution of necroptosis) and TUNEL assay will be performed for Apoptotic Index measurement. These biomarkers will be analyzed using immunohistochemical (IHC) techniques and the TUNEL method in rectal tissues obtained at baseline and the end of the intervention.

Procedures

Location

Biopsies will be collected at the baseline and final clinic visit in the Clinical Research Center (CRC) in Medical Center North, 3rd floor on the Vanderbilt Campus

Scheduling

Participants will be scheduled for the biopsies. All biopsy visits on a given participant will be scheduled for the same time of day to avoid potential variability due to circadian rhythm. A gastroenterologist trained in the procedure will take the biopsies in CRC procedure rooms.

Preparation

Prior to the arrival of the patient, study staff will prepare the following:

Proctoscopy supplies

- ID labels with the patient's ID number, date, and visit number
- 1 collection bottle filled with 10% normal buffered formalin
- Specimen container
- Plastic proctoscope
- Biopsy forceps, Cook 230 cm flexible biopsy forceps (2.4 mm cup diameter).
- Bowl of sterile normal saline
- Wash cloths
- 4x4's
- K-y jelly
- Magnifying glass
- Bath towel
- Gooseneck light
- Headband LED light
- Purple (nitrile) Gloves
- Rectal swabs
- Suction
- Toothpicks
- Disposable plastic spoon

Fresh rectal biopsy (non-paraffin imbedded):

- Cryo vials
- Insulated container
- Liquid nitrogen
- Dry Ice
 - Dry ice will be placed in an insulated bucket or container.
 - Plastic cup will be placed in dry ice to hold fresh tissue specimen
 - Place a small amount of dry ice into plastic cup
 - Cap the plastic container, until the cryovial with specimen is inserted.

Rectal biopsy for paraffin embedment

- Vials containing 10% normal buffered formalin

Rectal swabs

- Culturette swab and transport medium

Patient Arrival

- Review medication list
- Review supplement list
- Verify continued eligibility
- Verify Empty Rectal Vault (Recent bowel movement)
- Measure body size i.e., height, weight, hip and waist circumferences
- Answer questions
- **Take vital signs**
- Obtain informed consent and give the participant a written copy of the consent form
- Escort patient to the examining room and have them undress from the waist down and cover with a drape or gown. Notify the physician the patient is ready

Preparation for Biopsy

Procedure:

No fasting or bowel cleansing preparations is required. Participants are asked to have a bowel movement prior to arriving at clinic.

1. Patient is positioned in the Sims position
2. Insert culturette swab about 2 inches into rectum, rotate swab to collect fecal material, and carefully remove swab from rectum. Insert swab into the tube containing transport medium. (Do not use lubricant).
3. Biopsies are taken at 10 cm above the anal verge through a proctoscope using a large cup Cook flexible 230 cm biopsy forceps (2.4mm cup diameter).
4. Care is taken to place the fully open biopsy forceps at right angles to and against the mucosa in order to get a sample of sufficient area and depth.
 - At least **eight** adequate biopsies must be obtained
 - Study staff will examine biopsies with a magnifying glass to determine adequacy of biopsy
 - If a biopsy pinch is inadequate, another is obtained.
 - Do not remove the biopsy from the forceps using a needle or other instrument. Previously, we removed it with a pair of pincers, plastic (single use) or metal (sterilizable)
 - **Four to six** rectal biopsy specimens will be snap frozen for future analyses requiring fresh (non-paraffin imbedded) tissue. (**prepare the snap frozen tissue first !!**)
 - Place remaining biopsy specimens in labeled specimen bottle with 10% normal buffered formalin immediately.
 - If the biopsy cannot be teased off using the toothpick, shake it off in the normal saline, remove and put in formalin or in prepared green capped cryo vial
 - Biopsies can be retrieved from saline using a small plastic spoon
 - Record site of biopsy
 - Number of biopsies collected
 - Note any bleeding

Patient monitoring

After the biopsy, the patient is monitored for thirty minutes. The CRC staff will check blood pressure and have the patient go to the restroom to check for bleeding prior to leaving the clinic. Patient is told that they can expect some blood on the tissue on the day of the

biopsy. Bleeding heavier or more persistent than this should be reported. They should also report anal or lower abdominal pain, fever, a foul anal discharge, or anything else they think could be related to the biopsy. The gastroenterologists and the supporting medical team will handle emergencies. Any other problems discovered by the study team will be discussed at an appropriate level with the patient sufficient to affect referral to the patient's gastroenterologists or primary care physician who will also be informed after written consent by the patient.

Any unexpected anoscopy events (> Grade 1 pain events and any other complications to the biopsies) will be recorded on an Adverse Events Form; information will include a description of the complication, a rating of the severity, other essential information needed to evaluate the complication, an assessment of the likelihood that the event was due to a study procedure, and a statement of action taken. All potential complications of biopsies are rated as mild, moderate, or severe. Minor problems after the procedure are handled in consultation with the gastroenterologist, and recorded in the subject's study file. If undue complications of biopsies or other procedures arise, the study will be stopped ahead of schedule. In addition, in the event of a severe or life-threatening complication, the Vanderbilt Cancer Center Clinical protocol Review Committee will be immediately notified. Only participants with ongoing doctor/patient relationships will be used in this study. Patients will continue their usual care with the physician. Telephone numbers for the PI and study coordinator will be given to the participant. Emergencies will be handled by the gastroenterologist and supporting medical staff.

Rectal Swab processing

- At least 2 rectal swabs will be taken.
- Insert one swab into tube of transport media. Freeze the tube containing transport media and store the sample at -80°C until future analysis.
- Place another swab into culture media. Swirl and drain to side of culture media. Discard swab.
- Record the time of collection on BIOLOGICAL SAMPLE COLLECTION FORM (Appendix H).
- Send the sample to lab for immediate culture.
- All samples will be logged into a log sheet for that day, and signed off by respective personnel along their movement from the participant (retrieval, placing into freezing medium, transportation to the lab)

Biopsy Processing

Biopsy Collection

- 1-2mm wide and 1mm thick
- At least eight biopsies will be taken
- Remove from forceps by teasing off with toothpick or shaking into saline bowl
Biopsies can be retrieved from saline using a small plastic spoon
- Place fresh biopsy specimens into separate green capped vials and put vials into liquid nitrogen or dry ice. Place remaining biopsy specimens in labeled specimen bottle with 10% normal buffered formalin immediately.
- Enter the time the biopsies were dropped into formalin and / or snap frozen on the BIOLOGICAL SAMPLE COLLECTION FORM (Appendix H).

Laboratory Processing

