Aim 1: Conduct a randomized intervention trial (120 patients in each treatment or placebo arm) to evaluate the main effect of reducing the dietary Ca/Mg intake ratio to under 2.6 by magnesium supplementation on:

- 1) **Primary endpoints:** Increasing the expression of apoptosis biomarkers (e.g. TUNEL and Bax) and reducing expression of TRPM7, COX-2 (inflammation) and Ki-67 (proliferation index), pMLKL in colorectal mucosa.
- 2) **Secondary endpoints:** Increasing serum levels of magnesium and vitamin D and reducing plasma concentration of C-reactive protein. Reducing urinary excretion of prostaglandin E₂ metabolite (PGE-M). Increasing body magnesium store (magnesium tolerance test).

We hypothesize the reduction in the dietary Ca/Mg intake ratio among those with a high ratio may improve magnesium status, reduce magnesium transporter expression, reduce level of colorectal and systemic inflammation, increase colorectal apoptosis, reduce colorectal cell proliferation and, in turn, lead to a decreased risk of colorectal cancer.

Aim 2: Evaluate the interaction between magnesium treatment and the Thr1482Ile polymorphism (G→A). The intervention trial will be a 2-factor factorial design. The first factor is magnesium supplementation (modulation of the dietary Ca/Mg intake ratio). The second factor is the Thr1482Ile polymorphism genotype. Therefore, in either treatment or placebo arms (120 patients in each arm), we will randomly include 60 participants who carry the GG genotype and 60 participants who possess at least one A allele through genotype screening, then we will randomly assign them to the treatment or placebo arms with a 1:1 ratio. We expect to have about 10 subjects with AA genotype. For the AA carriers, the randomization will be stratified on genotype to ensure an equal number of AA genotypes will be assigned to the two arms.

We hypothesize that reducing the dietary Ca/Mg intake ratio will more significantly improve the body magnesium status and lead to more pronounced changes on primary endpoints among those who carry at least one variant A allele, particularly those with the AA genotype, compared to those who possess the GG genotype.

The focus of this proposed study is on the evaluation of gene-nutrient (Ca/Mg intake ratio) interaction in the development of colorectal cancer. The hypotheses proposed in the application are novel and based on strong biological plausibility and our recent findings from the TCPS and several other studies.

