A randomized controlled study is one in which there are two groups, one treatment group and one control group. The treatment group receives the treatment under investigation, and the control group receives placebo. Assigning patients at random reduces the risk of bias and increases the probability that differences between the groups can be attributed to the treatment. Randomization is used to determine who will receive the magnesium supplement and who will receive placebo treatment.

This study will enroll 288 participants with colorectal hyperplastic polyp or/and adenoma, polyps free but being at high risk of colorectal polyps or cancer. 152 of whom have the GG genotype and 136 of whom have GA/AA genotype. Within the two genotype groups, a permuted-block randomization algorithm will be used to allocate the subjects into the treatment/placebo arm.

Finally, these participants will be randomized to either treatment or placebo using a double-blind two-factorial (Ca/Mg intake ratio and genotype) design so that each treatment/placebo arm will contain 60 participants with the GG genotype and 60 participants with at least one A allele.

Procedures

- The Principal Investigator will generate a list of the 288 participants, 152 of whom have the GG genotype and 136 of whom have GA/AA genotype.
- [name], the co-PI, will conduct the randomization and provide a script to randomly allocate the participants into each treatment/placebo arm within the two genotype groups.
- Each treatment/placebo arm will contain 60 participants with the GG genotype and 60 participants with at least one A allele.
- Both the participants and the study staff will be blind to randomization status until the conclusion of the study. Pharmacists are un-blinded to randomization status and treatment assignment.

Intervention Protocol

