Base on our recently reported findings, the AA genotype would likely benefit the most from the magnesium supplementation. It is important to estimate the treatment effect within the three genotype groups and to compare the effects between the genotype groups. However, the AA genotype frequency is low (1.6%). We will be making every effort to enroll AA genotypes and expect to recruit 10 subjects during the 4 year recruiting period. Five each will be randomized to the treatment and the placebo group by stratifying on genotype groups. Due to the unequal number of subjects in the 2 by 3 ANOVA analysis, we conducted a simulation study to calculate the power for the interaction between the treatment and the GA genotype and the interaction between the treatment and the AA genotype. We used GG as the reference group. The power is 68% and 65%, respectively, with alpha=0.05. These separate powers are lower than the 0.94 power when GA and AA are combined since, besides the sample size difference, the simulation study allows us to use different standard deviations for the different subgroups of subjects, as opposed to a common standard deviation that has to be assumed by the method in the nQuery® software.

Data analysis plan: This study will adopt a 2X2 factorial design. The first factor is genotype (GG vs. GA/AA or GG vs. GA vs. AA) and the second factor is intervention (magnesium treatment: modulating dietary Ca/Mg intake ratio versus placebo). The primary endpoints, which are all continuous variables, include apoptosis biomarkers (e.g. TUNEL and Bax), and expression of TRPM7, COX-2 (inflammation) and Ki-67 (proliferation index), pMLKL in colorectal mucosa. The secondary endpoints include serum level magnesium, serum vitamin D, and plasma concentration of C-reactive protein as well as magnesium status (magnesium tolerance test), and urinary excretion of prostaglandin E₂ metabolite (PGE-M).

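### The written randomisation procedure names two genotype strata, which does not match the five-per-arm stratification of AA carriers in Aim 2 and in the power section

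*Combined protocol and SAP*

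**What the plan says.** **Operative procedure.** Section 6.0 E (Randomization Protocols) says "Within the two genotype groups, a permuted-block randomization algorithm will be used to allocate the subjects into the treatment/placebo arm", and section 5.0 has the same rule. The enrolled sample is described as "152 of whom have the GG genotype and 136 of whom have GA/AA genotype". The step for the randomising investigator is to "provide a script to randomly allocate the participants into each treatment/placebo arm within the two genotype groups". The target is that "each treatment/placebo arm will contain 60 participants with the GG genotype and 60 participants with at least one A allele". Neither section mentions an AA stratum or gives a block size.

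**Aim 2 (section 2.0).** After the 60/60 rule and the 1:1 allocation, the aim says of AA carriers that "the randomization will be stratified on genotype to ensure an equal number of AA genotypes will be assigned to the two arms". About ten such carriers are expected.

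**Section 9.0.** The power section repeats the AA commitment: "Five each will be randomized to the treatment and the placebo group by stratifying on genotype groups". It then gives simulated power of 68% for the GA interaction and 65% for the AA interaction, with GG as reference and alpha 0.05.

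**The concern.** The sections that state the purpose promise a balanced AA split. The sections that tell someone how to build the allocation list describe only two strata. Blocking within the combined GA/AA group balances carriers as a whole; it does not control how the few AA carriers among them fall between the arms.

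The AA group is small and cannot easily be topped up: section 9.0 puts its frequency at 1.6% and expects ten people over four years of recruitment. The same section expects AA carriers to benefit most, and the analysis plan commits to a separate AA estimate with a confidence interval. At stake are the precision of that estimate and the 65% figure, which assumes five per arm.

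**Working it through.** **Inputs**
- Carrier stratum: 136 enrolled, 120 completing (section 6.0 E); allocation 1:1 (Aim 2).
- AA carriers: 10, five per arm assumed for power (section 9.0).
- Placebo erythrocyte magnesium, mean and SD (Table D3): GG 5.25, 1.16; GA 4.61, 0.40; AA 3.7, with 0.40 borrowed from GA because n = 1.
- Treated means: 5.25 in GG and in carriers (section 9.0). Applying 5.25 to GA and AA separately is an assumption.
- SD of treated carriers: not stated, so several patterns were tried.

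**1. Reproduce the 2×2 figures.** Interaction contrast = 5.25 − 4.49 = 0.76. SE = SD × √(4/60).
- SD 0.83: SE 0.214, ratio 3.55, power Φ(3.55 − 1.96) ≈ 94% (stated 94%).
- SD 1.16: SE 0.300, ratio 2.54, power Φ(2.54 − 1.96) ≈ 72% (noncentral F 71.5%; stated 71%).

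**2. Reproduce the 65%.** AA interaction contrast = (5.25 − 3.7) − (5.25 − 5.25) = 1.55. Take 60 GG, 55 GA and 5 AA per arm, with SD 1.16 in GG and in treated carriers and 0.40 in placebo carriers.
- Pooled variance = [118(1.16²) + 58(1.16²) + 58(0.40²)]/234 = 1.052.
- SE used by the test = √[1.052 × (2/60 + 2/5)] = 0.675.
- Actual SE = √[2(1.16²)/60 + 1.16²/5 + 0.40²/5] = 0.588.
- Power ≈ Φ[(1.55 − 1.97 × 0.675)/0.588] = Φ(0.37) ≈ 65%. Simulation gives 64.5%.
- With 60 GA plus 5 AA per arm, simulation gives 68% (GA) and 65% (AA), matching both stated figures.

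At 5:5, the other SD patterns miss 65%: genotype SDs in both arms about 90%, common SD 0.83 about 81%, common SD 1.16 about 52%.

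**3. AA split under two strata.** With AA carriers in arbitrary positions in a balanced list of 136, the number allocated to magnesium is hypergeometric: P(k) = C(10,k) × C(126, 68−k) / C(136,68).

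| Split, either direction | Probability |
|---|---|
| 5:5 | 0.256 |
| 6:4 | 0.419 |
| 7:3 or worse | 0.325 |
| 8:2 or worse (included in the row above) | 0.096 |

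A stratum of 120 gives 0.257, 0.421, 0.322 and 0.095. Simulated permuted blocks of 2, 4, 6, 8 and 10 give 0.25–0.26 for 5:5, so block size does not matter here.

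**4. Power by split**, under the SD pattern that reproduces 65% (the range covers the two directions):

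| Split | AA interaction power |
|---|---|
| 5:5 | 64.5% |
| 6:4 | 62–64% |
| 7:3 | 56–58% |
| 8:2 | 44–46% |
| Average over splits | about 60% |

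The average loss is similar under the other patterns: about 90% to 84%, 81% to 76%, and 52% to 49%.

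**5. Precision of the within-AA difference**, with equal SDs in the two arms. Variance relative to 5:5 is (1/n₁ + 1/n₂)/(2/5): 1.19 at 7:3 and 1.56 at 8:2.

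**6. Dropout.** If 120 of 136 carriers complete and dropout is unrelated to genotype (an assumption), the probability that all ten AA carriers complete is the product of (120 − i)/(136 − i) for i = 0 to 9, which is 0.27. Under the step 2 SDs, average AA power is then about 58% with a 5:5 allocation and about 53% with two strata.

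**The case against.** A reader might infer that the trial will usually miss the 5:5 split, or that the allocation script contains the fault. The documents do not support that. The script is not included; the procedure says only that one will be provided. AA stratification is directed in two places. Aim 2 gives the two-group rule and the AA rule in the same paragraph, so the authors may see AA as a sub-stratum within the carriers, and an investigator following Aim 2 and section 9.0 would code it that way. This stands: the probabilities above are conditional on the written procedure being followed as it reads. The inconsistency also stands, because the only instructions for building the list name two groups.

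A second objection is that the loss is modest and the 65% is fragile. That also stands. A 5:5 or 6:4 split occurs about 67.5% of the time, at a cost of at most about 3 points. The AA mean comes from one pilot patient with a borrowed SD, and stated power moves between 52% and 90% across plausible SD patterns. Erythrocyte magnesium, on which the power rests, is called primary in the power section but is missing from the endpoint lists in Aim 1 and the data analysis plan.

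A third objection is that stratifying does not secure 65% among completers. This is correct: on the figures in step 6, dropout costs more than the missing stratum does. The gain from stratifying is still about 5 points.

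Finally, blocks of two in a ten-person stratum are easier to predict: one revealed assignment discloses its partner. Section 6.0 E describes prescriptions that carry both genotype and treatment assignment, so blinding reduces this risk without removing it.

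**Conclusion.** The inconsistency is real and worth correcting: sections 5.0 and 6.0 E name two strata, while Aim 2 and section 9.0 rely on AA being stratified. If the two-stratum text is applied literally to ten AA carriers, the promised 5:5 split occurs about one time in four, and AA interaction power averages about 60% instead of 65%. It drops to about 44–46% at 8:2; splits that uneven or worse have a probability of about 10%. The probabilities rest on ten AA carriers and 1:1 blocking within the carrier group. The power figures also rest on an inferred treated-carrier SD of 1.16.

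It would go too far to conclude that Aim 2 as a whole is compromised. The main treatment effect and the GG versus GA/AA interaction, with 60 per cell, are already protected by the two strata. Randomisation remains valid with either set of strata. What is affected is the precision of the AA results and the basis of the 65% figure.

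**What to change.** In sections 5.0 and 6.0 E, including the script step, replace the two genotype groups with three randomisation strata: GG, GA and AA.

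State a block size for the AA stratum that keeps the arms within one person of each other. Blocks of two do this for any AA total and give 5:5 with exactly ten. Blocks of four would not: ten carriers fill two blocks and half of a third, and that half is balanced with probability (2 × 2)/6 = 2/3, leaving a one-in-three chance of 6:4. Withhold the block size from recruiting staff and from anyone who does not need the allocation.

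Confirm that the script reads AA separately. If it already does, only the wording needs correcting. If enrolment has begun without it, apply the AA stratum to the remaining AA carriers and describe the 65% as conditional on a 5:5 split. In either case, note that dropout among AA carriers could lower the power.

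The cost is one extra stratum in the script and slightly greater predictability in a ten-person stratum. No extra participants are needed.
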